With the introduction of cardiac MRI for the assessment of atrial fibrosis in AF patients suffering from extensive LA remodeling without MVI, the identification of appropriate patients and therapy stratification for cardiac ablation and the associated clinical outcome was significantly improved.

To date, however, MVI patients suffering from LA remodeling have hardly been studied using these new imaging techniques. Therefore, we intend to combine advanced cardiac MRI and post-processing techniques prior to and after mitral valve repair surgery to gain more insight in the clinical implications of atrial fibrosis in this patient population.

It is hypothesized that the atrial fibrosis surface area paradoxically will increase after mitral valve surgery because of global shrinkage of the LA caused by the reversed remodeling process.[1] As a consequence, more frequently atrial fibrosis related events including (paroxysmal) AF, may be observed in these patients.

Objective: To assess the effects of (reduced) volume overload on the left atrial wall texture (presence, amount and location of atrial fibrosis) and associated geometry and function in patients with MVI, prior to and after mitral valve repair surgery.

Study design: Single center pilot study.

Study population: The research population consists of MVI patients scheduled for elective surgical mitral valve repair (N=20) according to the current European guideline criteria.

Image data from non-MVI/AF age-sex matched controls (N=10), retrieved from an existing database will be used for reference purposes. These controls have undergone the same MRI scan protocol for another indication.

Main study parameters/endpoints:

The main study parameters are:

1. Severity of MVI prior to and after surgery (defined as regurgitation volume in ml)
2. Left atrial remodelling prior to and after surgery
 - Left atrial volume
 - Calculated left atrial sphericity
 - Estimated wall tension (wall thickness, radius, pulmonary wedge pressure)
 - Mitral regurgitation flow measurement (quantitative)
3. Presence and distribution patterns of LA fibrosis
 - Quantification of fibrosis surface (severity)
 - Geometric distribution of fibrosis (localization)
4. Blood flow patterns in the left atrium (4D flow)
 - Flow velocity (mean and peak)
 - Static fraction
 - Kinetic energy

Nature and extent of the burden and risks associated with participation, benefit and group relatedness:

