1. INTRODUCTION AND RATIONALE

Patients with mitral valve insufficiency (MVI) frequently suffer from left atrial (LA) remodeling, caused by volume overload and subsequent atrial dilatation.[1]

The associated myocardial stretch and increased wall tension, trigger a cascade of pathways leading to the occurrence of atrial fibrosis as part of the remodeling process (*Figure 1*).[2] The clinical relevance of this atrial fibrosis, is that its presence is associated with an increased risk of atrial fibrillation (AF), heart failure (HF), pulmonary hypertension (PH), a reduced quality of life and eventually a shorter life expectancy.[3, 4] In addition, in patients suffering from atrial fibrillation (AF), the presence and amount of LA fibrosis was found to be a strong predictor for ablation efficacy and long-term outcome.[5, 6]

In daily clinical practice, MVI is managed either by medical or surgical therapy.[7] However, since medical therapy is often not sufficient for patients with severe primary MVI, surgical intervention remains the ultimate treatment option for these patients. In general, valve repair is the preferred type of surgery, since it has better clinical results compared to valve replacement.[8]

Currently, the indication and timing for valve surgery is mainly based on the severity of MVI and the presence of symptoms and/or severity of left ventricular dysfunction.[9]

For clinical decision making and patient stratification for mitral valve surgery, the presence of atrial fibrosis is currently not taken in account, despite its well-recognized clinical implications.

Detection of atrial fibrosis patterns in patients with severe MVI, however, may be potentially valuable for the indication and timing of mitral valve repair surgery to improve clinical outcomes. Improved insight into atrial fibrosis patterns and changes after mitral valve repair due to reverse remodeling, may help clinicians in their clinical decision making and timing for surgery.

Today, quantification of atrial fibrosis can be routinely performed using cardiac magnetic resonance imaging (CMR) techniques and advanced post-processing tools, offering non-invasive tissue characterization in thin-walled structures.[6]

To date, MVI patients suffering from LA remodeling have hardly been studied using these new imaging techniques. Therefore, in this study, we want to combine advanced cardiac MRI and

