2. OBJECTIVES

Primary Objective:

To assess

- the effects of (reduced) volume overload on the left atrial wall texture (presence, amount and location of atrial fibrosis) and associated geometry and function in patients with MVI, prior to and after elective mitral valve repair surgery.

Secondary Objectives:

To assess;

- the value of LA fibrosis in stratification and timing of mitral valve repair surgery.
- the impact of atrial fibrosis on myocyte contractile function (atrial strain, quantified by CMR).
- whether left ventricular (LV) volume overload results in increased extra cellular volume (ECV) and whether this is reversible after mitral valve repair surgery.
- the impact of LA remodeling on right atrial (RA) function and tissue characteristics.
- the predictive value of LA fibrosis for outcomes of AF and atrial function during post-surgical follow up

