3. STUDY DESIGN

This study is designed as a single center pilot study. The aim of this study is to assess the role of left atrial fibrosis and its characteristics prior to and after mitral valve repair surgery in MVI patients.

Study subjects that will be included are MVI patients who meet the criteria for mitral valve repair surgery and are on the waiting list for elective surgery. Exclusion criteria are: AF, history of cardiac surgery, comorbidities, MRI contra-indications. The study subjects are recruited from the Amsterdam UMC surgical waiting list.

The study subjects will visit the AmsterdamUMC hospital (Location VUmc) two weeks prior to mitral valve repair surgery for a CMR scan. This visit will start with checking in- and exclusion criteria using questionnaires regarding medical history and MRI safety. The total duration of the visit, including the CMR scan, will be approximately two hours.

[figure not shown]
Two weeks later the subjects will undergo mitral valve repair surgery (Location AMC). During anesthesia, a Swan-Ganz catheter will be used for hemodynamic monitoring. This Swan-Ganz catheter is part of the standard care for mitral valve repair surgery.

At three months follow-up, subjects will visit the AmsterdamUMC hospital (Location VUmc) for a second CMR scan to assess reversed atrial remodeling and amount of fibrosis.

Image data from age and gender matched controls will be retrieved from an existing database. The patients in this database have undergone the same MRI scan protocol (for a different medical indication) as scheduled for our study population. Only data from patients without MVI and AF will be used from the database for reference. Absence of MVI and AF will be confirmed by checking ECGs and echocardiography of the control patients.

See *figure 2* for a schematic representation of the study design.

Figure 2. Schematic representation of the study design: Left atrial remodeling in MVI

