5. METHODS

5.1 Study parameters/endpoints

5.1.1 Main study parameter/endpoint

The main study parameters are:

1. Severity of MVI prior to and after surgery (defined as regurgitation volume in ml)
2. Left atrial remodelling prior to and after surgery
 - Left atrial volume
 - Calculated left atrial sphericity
 - Estimated wall tension (wall thickness, radius, pulmonary wedge pressure)
 - Mitral regurgitation flow measurement (quantitative)
3. Presence and distribution patterns of LA fibrosis
 - Quantification of fibrosis surface (severity)
 - Geometric distribution of fibrosis (localization)
4. Blood flow patterns in the LA (4D Flow)
 - Flow velocity (mean and peak)
 - Static fraction
 - Kinetic energy

Secondary study parameters/endpoints -Fibrosis associated biomarkers derived from blood samples (NT-proBNP, TNF- β , Angiotensin II, cytokines)

-Heart failure symptoms monitoring derived from questionnaire preoperative and at postoperative follow-up

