In the occurrence of a clinical relevant incidental finding patients will be informed by their treating physician. During the informed consent patients will be notified of this obligation. Patients who refuse to be informed about clinical relevant incidental MRI findings, will be excluded from this study.

MRI processing

Quantification of LA fibrosis will be performed using commercially available ADAS 3D LA image post-processing software (Galgo Medical, Barcelona, Spain) and open-source CEMRG image post-processing software (King's College London, United Kingdom). The 3D LGE images will undergo stringent quality control (i.e. artefacts, proper myocardial nulling) by two experienced readers prior to post-processing and images will be excluded from analysis if quality is deemed insufficient.

[figure not shown]

Figure 3. Left atrial 3D reconstruction from MRI.

Left Atrial remodeling

LA remodeling will be assessed by quantifying atrial sphericity and calculation of the wall tension calculation using Laplace's law ($T = p \times r / 2T$). This calculation includes pulmonary wedge pressure which is determined using peri-operative Swan-Ganz based pressure measurements during anesthesia, and radius based on atrial volume and wall thickness. Also the relation to quantitative MVI will be determined using 4D-flow MRI processing.

Presence and distribution of LA fibrosis

Quantification of fibrosis surface and the distribution of fibrosis will be assessed using LA 3D reconstructions based on 3D MRA data. Output of this data will be as shown below in Figure 4. The left atrial wall is segmented for accurate geometric localization of fibrosis (*Figure 4A*) and the severity of fibrosis will be shown as quantified surface area (*Figure 4B*).

[figure not shown]

Figure 4. Left atrial segmentation (A) for accurate assessment of geometric distribution of fibrosis and severity of fibrosis shown as quantified surface (B).

4D Flow

4D-flow data will be corrected for Maxwell terms in the image reconstruction at the scanner, and velocity aliasing during post-processing. 4D flow data will be co-registered with the cine images to guide left atrial anatomic orientation. Mean and peak flow velocity data will be derived using dedicated research software (MASS version 2017-Exp, Leiden University Medical Center, Leiden, the Netherlands). Furthermore, the volume fraction in the left atrium with a flow velocity below 10cm/s during the entire cardiac cycle will be determined.

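### Left atrial wall tension is listed as a before-and-after measure, but its only planned pressure is the operative wedge, so a three-month value would join operative pressure to three-month geometry

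*Combined protocol and SAP*

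**What the plan says.** The Summary and section 5.1.1 set out the main study parameters. The second is "Left atrial remodelling prior to and after surgery", and one of its four components is "Estimated wall tension (wall thickness, radius, pulmonary wedge pressure"). Nothing there restricts this component to the pre-operative time point.

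Section 5.2 (Left Atrial remodeling) computes the tension by Laplace's law, with a radius based on atrial volume and wall thickness. On pressure it says: "This calculation includes pulmonary wedge pressure which is determined using peri-operative Swan-Ganz based pressure measurements during anesthesia".

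Section 3 fixes the timing:

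- The first CMR is two weeks before the operation.
- "Two weeks later the subjects will undergo mitral valve repair surgery", and "During anesthesia, a Swan-Ganz catheter will be used for hemodynamic monitoring". The catheter is described as standard surgical care.
- "At three months follow-up, subjects will visit the AmsterdamUMC hospital (Location VUmc) for a second CMR scan to assess reversed atrial remodeling".

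The other follow-up items are blood samples at three months (section 5.2) and a postoperative heart failure symptom questionnaire (section 5.1.1). No wedge pressure, catheterisation or non-invasive pressure estimate is described at either scan.

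**The concern.** Wall tension by Laplace's law needs pressure, radius and thickness from the same state of the atrium. The plan supplies geometry on two occasions and pressure only at a third, under anesthesia. For a three-month value, the pressure would come from an operation about three months earlier. The text also does not say which operative reading belongs with which scan.

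This matters because of how the result would be read. The introduction gives tension a causal role: "The associated myocardial stretch and increased wall tension, trigger a cascade of pathways leading to the occurrence of atrial fibrosis". The primary objective is to assess "the effects of (reduced) volume overload on the left atrial wall texture" and on atrial geometry and function. A before-and-after wall tension invites reading as the load result that connects the two, yet the planned data say nothing about pressure at three months.

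Section 7.1 names no wall-tension contrast, but it plans means with standard deviations and correlation analyses. In a post-operative or change value entered there, the carried operative pressure would act as a patient-specific multiplier unrelated to any later change in pressure.

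**Working it through.** The documents state no wall-tension or pressure figure, so there is none to reproduce. The check is the algebra of the planned formula, followed by an illustration.

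**Formula.** Section 5.2 prints T = p × r / 2T, with one letter for two quantities. Read with *h* as wall thickness, it is T = p × r / (2h). Hence

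T_post / T_pre = (p_post / p_pre) × (r_post / r_pre) × (h_pre / h_post).

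**One operative reading used at both times.** Then p_post / p_pre = 1, and the ratio reduces to (r_post / r_pre) × (h_pre / h_post). The percent change contains no pressure information. The absolute change, with constant *h*, is p × (r_post − r_pre) / (2h): the geometric change multiplied by the patient's operative pressure.

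**Illustration. Every input is assumed; none is in the documents.** Atrial volume falls 30%, shape is constant (radius as the cube root of volume) and thickness is constant.

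- Radius factor: 0.70^(1/3) = 0.888.
- Carried pressure: 0.888 × 1.0 − 1 = -11%, whatever the true pressure does.
- True three-month pressure 0.8 times operative: 0.888 × 0.8 − 1 = -29%.
- True pressure 0.6 times operative: 0.888 × 0.6 − 1 = -47%.
- True pressure unchanged: -11%, so no error.
- Pressure rise that cancels the whole geometric change: 1 / 0.8879 − 1 = 12.6%, or 1.9 mmHg at an assumed 15 mmHg.

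**Other volume falls, carried pressure.** A fall of 10% gives -3.5% and a fall of 40% gives -15.7%, again whatever the true pressure does.

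**Choice of operative reading.** If readings before and after the repair both exist and are paired with the two scans, assumed post-/pre-repair ratios of 0.8, 1.0 and 1.2 give -29%, -11% and +7% on the same geometry. A single carried reading gives -11% each time.

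**Absolute change.** Take 120 to 84 mL as a sphere, so the radius goes from 3.060 to 2.717 cm, with a 0.2 cm wall. The multiplier is (2.717 − 3.060) / 0.4 = -0.857. An operative wedge of 10 mmHg gives -8.6 mmHg and one of 20 mmHg gives -17.1 mmHg. This is a two-fold difference between patients with identical remodelling.

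**Shape and thickness.** If shape changes and the radius factor lies anywhere from 0.80 to 1.00, the carried result runs from -20% to 0%. With pressure down 40%, it would be -52% (0.80 × 0.6 − 1) to -40% (1.00 × 0.6 − 1). If wall tissue volume were conserved instead, the wall would thicken as the atrium shrinks, and the carried result in the 120 to 84 mL example would be about -28%. The level moves with these assumptions, but the absence of pressure information does not.

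**The case against.** The strongest reply is that the mismatch is inferred. The before-and-after wording heads a group of four components, while section 5.2 describes one calculation and states no three-month tension. A pre-operative-only value would fit section 5.2. If that is the intention, however, the main-parameter list says otherwise and needs the same correction. Section 3 also says the three-month scan is there to assess reverse remodelling, and section 5.2 makes this calculation part of how remodelling is assessed.

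A second reply is that section 5.2 speaks of measurements in the plural, so readings before and after the repair may exist. Pressure would then not cancel. Even so, the later reading would still be taken under anesthesia about three months before the second scan, and no pairing rule is given.

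Three points stand and limit the weight of the finding:

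- The primary objective concerns volume overload, which is measured directly before and after surgery by regurgitant volume, flow and atrial volume. Wall tension is one estimated component.
- Relating pre-operative tension to fibrosis is a reasonable use of the operative wedge. The time gap is about two weeks, and scaling by pressure is what Laplace's law intends. The objection is to the post-operative and change values.
- The percentages depend on assumed inputs, including wall thickness. They show dependence on unknowns, not an expected bias.

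A lighter remedy, stating which pressure enters each time point, would make the calculation explicit. It would not make the result a measure of three-month load.

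**Conclusion.** The concern holds. As written, any three-month pressure-based wall tension would use a pressure from the operation, and no use of the planned data supplies a valid one. With a single carried reading, the percent change is a geometric change under another name, and the absolute change is that geometry scaled by operative pressure.

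The size cannot be known from the documents. Under the base illustration, a reported -11% would be compatible with true changes from -11% to -47% if pressure fell by up to 40%, and with no change at all if pressure rose by 12.6%.

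The textual facts are clear. How readers would interpret the value is a judgement. Figure 2, the study schematic, was not available, so the conclusion rests on the text. One component of one main parameter is affected. Fibrosis, volume, sphericity, flow and the planned 20 patients are not. It should be fixed before analysis, partly so that the choice among operative readings is not made after results are seen.

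**What to change.** 1. In the Summary and sections 5.1.1 and 5.2, limit the pressure-based wall tension to the pre-operative/operative time point. Name the operative reading that is paired with the pre-operative CMR, and state as a limitation that it is taken under anesthesia about two weeks after that scan.
2. Report the before-and-after comparison on geometry: atrial volume, radius and sphericity.
3. If a post-operative tension is still shown, label it exploratory, name the operative reading used, and state that it is not interpreted as a change in haemodynamic load.
4. For clarity, say how wall thickness is measured and use separate symbols for tension and thickness.

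The cost is protocol wording and notification of the amendment to the METC (section 9.2). No visit or measurement is added. The sponsor gives up, or relabels as exploratory, one post-operative component of a main parameter.

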5.3 Withdrawal of individual subjects

Subjects can leave the study at any time for any reason if they wish to do so without any consequences. The investigator can decide to withdraw a subject from the study for urgent medical reasons. This will be correlated with CMR derived LA fibrosis.

5.4 Replacement of individual subjects after withdrawal

Upon withdrawal of a subject, the data collected will not be used for the study and will be deleted.

5.5 Follow-up of subjects withdrawn from treatment

Not applicable.

5.6 Premature termination of the study

Study participants can withdraw their consent at any time during the MRI protocol. However, since patients with claustrophobia will not be included in the study, it is unlikely that patients who have agreed to participate will withdraw during the 45 min MRI protocol. In addition, since all the elements of this study are harmless and carry no risk, it is unlikely that this will occur.

5.7 Potential risk analysis due to COVID-19 regulations

The main risk for our study due to unexpected upscaling of COVID-19 regulations would be the delay of elective surgical mitral valve repair procedures. This would be due to a (temporary) reduced intensive care unit capacity. However, this would not impact the study feasibility, as a consequence the study will take longer to include the target number of inclusions. Other study related procedures would not be affected by COVID-19 as these are reserved for research purposes.

6. SAFETY REPORTING

6.1 Temporary halt for reasons of subject safety

In accordance to section 10, subsection 4, of the WMO, the researchers will suspend the study if there is sufficient ground that continuation of the study will jeopardise subject health or safety. The researchers will notify the accredited METC without undue delay of a temporary halt including the reason for such an action. The study will be suspended pending a further positive decision by the accredited METC. The investigator will take care that all subjects are kept informed.

6.2 AEs and SAEs

6.2.1 Adverse events (AEs)

Adverse events are defined as any undesirable experience occurring to a subject during the study considered related to MRI procedure. All adverse events reported spontaneously by the subject or observed by the investigator or his staff will be recorded.

6.2.2 Serious adverse events (SAEs)

A serious adverse event is any untoward medical occurrence or effect that

- results in death;
- is life threatening (at the time of the event);
- requires hospitalisation or prolongation of existing inpatients' hospitalisation;
- results in persistent or significant disability or incapacity;
- is a congenital anomaly or birth defect; or
- any other important medical event that did not result in any of the outcomes listed above due to medical or surgical intervention but could have been based upon appropriate judgement by the investigator.

An elective hospital admission will not be considered as a serious adverse event.

The additional risks associated with participation in this study are considered minimal. Gadolinium is a safe contrast agent, which is frequently used in clinical practice. Intravenous gadolinium administration may cause minimal injection site reactions (e.g. pain, cold or burning sensation). As with other contrast-agents, anaphylactic-like reactions can occur, although this is very unusual.

Nevertheless, the investigators will report all SAEs to the accredited METC without undue delay after obtaining knowledge of the events. The researchers will report the SAEs through the web portal *ToetsingOnline* to the accredited METC that approved the protocol, within 7 days of first knowledge for SAEs that result in death or are life threatening followed by a period of maximum of 8 days to complete the initial preliminary report. All other SAEs will be reported within a period of maximum 15 days after the researchers have first knowledge of the serious adverse events.

